Methodology: This Phase 3 study design includes the Screening Period followed by a 12-Week double-blind Induction Study and 44-Week double-blind Maintenance Study. The Induction Study will assess the efficacy and safety of two adalimumab induction regimens in achieving clinical remission, defined as Crohn's Disease Activity Index (CDAI) $< 150$ at Week 4, and endoscopic response, defined as a decrease in Simplified Endoscopic Score for Crohn's Disease (SES-CD) $> 50\%$ from Baseline (or for a Baseline SES-CD of 4, at least a 2 point reduction from Baseline), as scored by central reviewer, at Week 12; in subjects with moderately to severely active Crohn's disease and evidence of mucosal ulceration at Baseline. The Maintenance Study will assess the efficacy and safety of two adalimumab maintenance regimens in maintaining clinical and endoscopic improvements at Week 56. Analyses of the outcomes from the maintenance regimens are considered exploratory. During both the Induction Study and the Maintenance Study, visit week designations will represent weeks since first dose in the Induction Study. Week 0 (Baseline) will reflect the date of first adalimumab dosing in the Induction Study. Week 12 will represent the final assessment in the Induction Study. Week 56 will represent the final assessment in the Maintenance Study (representing 44 weeks of maintenance treatment in the Maintenance Study).	

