**Table 3. Study Activities (Continued)**

Activity	Screening Period (30 Days) a	12-Week Double-Blind Induction Study						44-Week Double-Blind Maintenance Study								Unscheduled Visit y	70-Day Follow-Up t				
		Baseline	Week 2	Week 4	Week 6	Week 8	Week 12 (Re-Randomization)	Week 14	Week 20	Week 26	Week 28	Week 34	Week 40	Week 42	Week 48			Week 56/Premature Discontinuation			
Dispense Subject Diary	X																				
Subject Diary Review		X	X	X	X	X	X	X	X	X	X	X	X	X	X	X	X	X	X	X	X
Intestinal Biopsies p	X						X														

- a. The Screening period will be a minimum of 7 days for CDAI calculation. The CDAI calculated at Screening will serve as the Baseline CDAI. Baseline visit date will serve as the reference for all subsequent visits. A ± 3-day window is permitted around all study visits.
- b. Update inclusion/exclusion, prior and concomitant therapy, and medical/surgical history information to assure subject eligibility.
- c. Height will be measured at Screening only (with shoes off, and then adding 1 inch or 2.5cm).
- d. An ileocolonoscopy will be performed during Screening or one performed within 45 days before Baseline, Week 12, and at Week 56/PD. A biopsy will be performed at Screening, Week 12, and Week 56/PD if a suspicious lesion or suspected malignancy, in the assessment of the Investigator, is observed, and evaluated by the local pathologist. Site staff should schedule the Week 12 Endoscopy during the Baseline visit, if possible. Appropriate documentation of biopsy results consistent with the diagnosis of CD, in the assessment of the Investigator, must be available in order to confirm the subject's eligibility for the study. If this documentation is not available, a diagnostic biopsy from the most affected observed area of the ileum/colon must be performed during the Screening endoscopy and evaluated by a qualified local pathologist and the results reviewed by the Investigator. Biopsies to evaluate suspicious lesions and to rule out malignancy may be taken during any study endoscopy per the Investigator's discretion and evaluated by the local pathologist.

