Subjects should administer study drug on the same day of the week. The dosing dates for all doses of study drug should be calculated from the Baseline Visit date. A  $\pm 3$ -day window is allowable for scheduled study dosing dates. For subjects that deviate from this dosing window, every effort should be made to bring the subject back to the original dosing schedule as soon as possible. For situations where bringing the subject back on the original dosing schedule will cause the dose to be out of the  $\pm 3$ -day window, please contact the AbbVie SDP for additional instructions.

At all office visits, subjects should be observed after study drug administration until judged clinically stable by the study personnel. If an anaphylactic reaction or other serious allergic reaction occurs, administration of study drug should be discontinued immediately and appropriate therapy initiated. When dosing at home subjects should be instructed to contact the site immediately with any signs or symptoms of a reaction. If subjects are unable to reach their study site or experience life-threatening symptoms, they will be instructed to call an emergency number or proceed to the nearest emergency room and then inform the site as soon as possible.

Subjects will be instructed to return all used and unused syringes, sharp containers and empty boxes at each visit for accountability.

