6.0 Analysis Conventions

Definition of Induction Baseline

The Induction Baseline visit date is the date when the first dose of study drug is received and referred to as Day 1 or Week 0. If a subject has not taken any study drug during Induction Study, the randomization date will be used as Day 1. The Baseline value for a variable is defined as the last non-missing value on or before the date of the first dose of study drug.

Definition of Maintenance Baseline

The Maintenance Baseline visit date is the date when the first dose of study drug during Maintenance Study is received and referred to as Day 1 of Maintenance Study or Week 0 of Maintenance Study. If a subject has not taken any study drug during Maintenance Study, the re-randomization date will be used as Day 1. The Maintenance Baseline value for a variable is defined as the last non-missing value on or before Day 1 of Maintenance Study, and after the Induction Baseline.

Definition of Maintenance Final Observation

Final Observation in the 56-week period (44-week double-blind Maintenance Study) is defined as the last non-missing observation collected within 70 days following the last dose of study drug who are re randomized.

Definition of Rx Days (Days Relative to the First Dose of Maintenance Study Drug)

Rx Days are calculated for each time point of interest and it provides a quantitative measure of days between the event and the first dose date. That is, the Rx Day is calculated as the event date minus the date of first dose of study drug plus 1. The Rx Day will be a negative value when the time point of interest is prior to the date of first dose of study drug, and the Rx Day will be a positive value when the time point of interest is after

the first dose date. By this calculation algorithm the first dose day is Rx Day 1 of Maintenance Study, while the day prior to the date of first dose is defined as Rx Day –1 of Maintenance Study (there is no Rx Day 0). Rx Days are used to map actual study visits to the protocol specified study visits.

Dealing with Multiple Measurements Collected on the Same Day

For efficacy related analyses, if multiple measurements for a particular parameter are collected on the same day for the same subject, the average of those measurements will be used.

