For safety related analyses, if multiple measurements are made for a particular laboratory or vital sign parameter on the same day for the same subjects, the one with later time will be used if collection time is also available, or the average of the values will be used in the analyses of change from Baseline. For summaries and listings for shift from baseline and potentially significant values, all collected values within the pre-specified treatment window will be used.

Definition of Analysis Windows

Since subjects do not always adhere to the study visit schedule, the following rules will be applied to assign actual visits to protocol-specified visits including early termination visits. For each study visit mentioned in the protocol, a nominal or target day will be selected to represent the corresponding visit along with a window around the target day. Windows will be selected in a non-overlapping fashion so that a date collected on the CRF does not correspond to multiple visit windows. Moreover, windows will not discard any Post-Baseline measurement recorded on the CRF. If a subject had two or more actual visits in one visit window, the visit closest to the schedule visit will be used as the study visit for that window. If two visits are equidistant from the target, then the later visit will be used for reporting. If more than one assessment is collected on the same day, then the average of those assessments will be used in analyses.

Table 3. Visit Windows for Analysis of CDAI and Vital Signs for Maintenance Study

Scheduled Week	Nominal Day	Time Window (Rx Day Range)
Week 12 (Week 0 of Maintenance Study)	1 ^a	≤ 1
Week 14 (Week 2 of Maintenance Study)	15	2 – 36
Week 20 (Week 8 of Maintenance Study)	57	37 – 78
Week 26 (Week 14 of Maintenance Study)	99	79 – 106
Week 28 (Week 16 of Maintenance Study)	113	107 – 134
Week 34 (Week 22 of Maintenance Study)	155	135 – 176
Week 40 (Week 28 of Maintenance Study)	197	177 – 204
Week 42 (Week 30 of Maintenance Study)	211	205 – 232
Week 48 (Week 36 of Maintenance Study)	253	233 – 281
Week 56 (Week 44 of Maintenance Study)	309	282 – 379

Rx Day = date of visit – date of first study drug injection in double-blind maintenance study + 1

- a. Day of first dose of study drug in double-blind maintenance study. If a subject has not taken any study drug during Maintenance Study, the randomization date will be use as Day 1 of Maintenance Study.

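### Maintenance visits are scheduled from Week 0 but windowed from the first maintenance dose, so a dose 7 to 20 days late leaves the Week 28 and Week 42 CDAI windows without a scheduled visit

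*Protocol*

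**What the plan says.** The protocol uses one calendar for both periods. Its synopsis states that "visit week designations will represent weeks since first dose in the Induction Study". Protocol Table 3 (Study Activities), footnote a, adds that "Baseline visit date will serve as the reference for all subsequent visits" and that "A ± 3-day window is permitted around all study visits"; footnote a of Maintenance SAP Table 2 says the same. Dosing follows this calendar too: under Study Drug Dispensing/Administration in protocol section 5.3.1.1, "The dosing dates for all doses of study drug should be calculated from the Baseline Visit date", and a subject who drifts is to be brought back to the original schedule.

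Section 6.0 of the Maintenance SAP starts a second clock. "The Maintenance Baseline visit date is the date when the first dose of study drug during Maintenance Study is received", and Table 3, which covers CDAI and vital signs, uses "Rx Day = date of visit – date of first study drug injection in double-blind maintenance study + 1". A typical row, giving visit, nominal day and range, is "Week 26 (Week 14 of Maintenance Study) 99 79 – 106". When two visits share a window, the one nearer the target is used; "If two visits are equidistant from the target, then the later visit will be used for reporting". No rule keeps a visit's protocol label. Missing binary outcomes count as failures (NRI). For continuous endpoints LOCF is the primary method.

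**The concern.** The two clocks agree only when the first maintenance dose falls on its scheduled day. If the dose is late but later visits stay on the protocol calendar, every visit has a smaller Rx Day than Maintenance SAP Table 3 expects. The weak points are the pairs only two weeks apart, Weeks 26/28 and 40/42, where the boundary lies 7 days from each target.

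At stake are the binary CDAI endpoints listed at each scheduled maintenance visit: remission, clinical response and enhanced clinical response. A subject who attended Week 28 in remission could be counted as a failure at Week 28, with that same measurement reported as Week 26. By-visit vital-sign summaries would carry the same wrong labels.

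Late first maintenance doses can be foreseen from the documents. Re-randomisation is stratified on the site's Week 12 endoscopy score, so a late endoscopy can hold it up. Protocol section 6.1.7 interrupts injections for serious infection and around surgery. The Induction SAP lets the Week 12 windows run to Day 98 (CDAI), Day 112 (fecal calprotectin) and Day 168 (SES-CD), each capped relative to the first maintenance or extension-study dose.

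**Working it through.** **Inputs.** Visit calendar: protocol synopsis and Table 3, footnote a. Windows and selection rules: Maintenance SAP section 6.0 and Table 3. NRI and LOCF: Maintenance SAP sections 6.0 and 10.2.

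**The SAP's own table.** Every nominal day equals 7 × (week − 12) + 1; for example, Week 28 gives 7 × 16 + 1 = 113. Each upper limit from Week 14 to Week 48 is the midpoint of adjacent nominal days: (99 + 113)/2 = 106 and (197 + 211)/2 = 204. The table is internally consistent, on the premise that the first maintenance dose falls on study Day 7 × 12 + 1 = 85.

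**With a late dose.** Let the first maintenance dose fall on Day 85 + d and let the Week w visit fall on its target, Day 7w + 1. For visits after the dose:

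Rx Day = (7w + 1) − (85 + d) + 1 = 7(w − 12) + 1 − d.

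Week 28 is therefore at 113 − d and Week 42 at 211 − d.

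| d | Week 26 visit | Week 28 visit | Week 40 visit | Week 42 visit |
|---|---|---|---|---|
| 6 | 93 | 107 | 191 | 205 |
| 7 | 92 | 106 | 190 | 204 |
| 10 | 89 | 103 | 187 | 201 |
| 20 | 79 | 93 | 177 | 191 |

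The Week 26 window is 79–106 and the Week 28 window 107–134; Week 40 is 177–204 and Week 42 is 205–232. At d = 6 all four visits are placed correctly. At d = 7 both visits of each pair fall in the earlier window. Each is 7 days from the target (99 or 197), so the tie rule takes the later one. From d = 8 to 20 the later visit is closer (at d = 10, 4 days against 10). The true Week 26 and Week 40 values go unused, and the Week 28 and Week 42 windows hold no scheduled visit.

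**From 14 days.** The Week 14 visit then falls on or before the first maintenance dose, so for d = 14 to 20 the Week 14 window is empty as well.

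**From 21 days.** The Week 34 visit (155 − 21 = 134) and the Week 48 visit (253 − 21 = 232) enter the Week 28 and Week 42 windows. Those windows are then mislabelled, not empty. For d = 21 to 27 the empty window is Week 48. For d = 28 to 34 it is Week 56, because 309 − 28 = 281 is the last day of the Week 48 window.

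**Visit tolerance.** If visits run 3 days early, the threshold falls to d = 4; if 3 days late, it rises to d = 10. With both dose and visits inside tolerance, the worst case (dose 3 days late, visit 3 days early) gives 113 − 6 = 107 and 211 − 6 = 205. Both are still correct.

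**Scoring.** In the empty windows NRI records failure for binary endpoints unless an unscheduled visit supplies a value. Under LOCF the Week 28 gap is filled from the Week 26 window, which now holds the Week 28 measurement, so the error there is the label at Week 26. Observed-case analysis simply omits the subject.

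**Unscheduled visits.** For d = 7 to 20, unscheduled visits at Week 30 (Rx Day 120 to 107) and Week 32 (134 to 121) lie in the Week 28 window. Those at Week 44 (218 to 205) and Week 46 (232 to 219) lie in the Week 42 window. Protocol section 5.3.1.1 requires CDAI at unscheduled visits, so any of these would fill the gap.

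**The case against.** The strongest reply is that no compliant subject is affected: the dose must be at least 4 days late, and the visits must then return to the original calendar. That is correct. But the SAP gives non-adherence to the schedule as its reason for having analysis windows, so this is the case they must handle.

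Counting from the first maintenance dose is also a defensible choice, since it measures time on the re-randomised regimen. It does not fit visits that the protocol schedules on another clock.

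Long delays strain the model. From 14 days late, a Week 14 visit on its target day would fall on or before the first maintenance dose, which is hardly a workable schedule. The results at 14 days and above depend on visits staying on target regardless.

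Four stronger readings are tempting and are not supported:

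- A reader might infer that any delay of 7 days or more makes Weeks 28 and 42 failures. That holds for 7 to 20 days, for binary endpoints under NRI, and with no unscheduled visit in the window.
- A reader might infer that late Week 12 visits are expected because the Induction SAP windows are wide. Window width shows that lateness is allowed for, not how common it is.
- A reader might put a size on the bias by multiplying the share of subjects with an empty window by their remission rate. The documents give neither figure.
- A reader might see a breach of the SAP's assurance that windows discard no post-Baseline measurement. The same paragraph goes on to choose one visit when two share a window, so unused values are foreseen.

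A difference between arms is possible, because escalation at unscheduled visits is described only for the clinically adjusted regimen and those visits can fill the gap. Nothing shows that it would be material.

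**Conclusion.** The conflict between the protocol calendar and Maintenance SAP Table 3 is real. For visits on their target days the 7-day threshold is exact. A first maintenance dose 7 to 20 days late puts wrong-week values at Weeks 26 and 40 and leaves Weeks 28 and 42 without a scheduled visit. For binary CDAI endpoints this turns attended visits into failures unless an unscheduled visit intervenes. Longer delays move the gap to Week 48 or Week 56.

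The importance is low. All maintenance efficacy endpoints are exploratory and non-ranked. With visits on target, Week 56 CDAI is affected only from 28 days late. The wider windows for SES-CD, questionnaires and laboratory values are not affected at 7 to 20 days. The frequency of such delays is not given, so no size of bias can be stated. The point deserves correction because the error is systematic where it occurs and cheap to remove.

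**What to change.** In Maintenance SAP Table 3, assign visits dated after the first maintenance dose by study day from Induction Day 1, and add 84 days to the present post-baseline limits:

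- Week 26: Days 163–190 (target 183)
- Week 28: Days 191–218 (target 197)
- Week 40: Days 261–288 (target 281)
- Week 42: Days 289–316 (target 295)

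Treat the other rows in the same way. On-target Week 28 and Week 42 visits, at Days 197 and 295, then stay in their own windows whatever the delay, provided they fall after the first maintenance dose. Keep the first maintenance dose as Day 1 for Maintenance Baseline, exposure and time to dose escalation.

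The cost is a table edit and a programming change; trial conduct does not change. There are two drawbacks. The SAP would run two clocks, which it should state plainly. In a late subject, a given week's value would also reflect less time on the re-randomised regimen: with a dose 13 days late (Day 98), the Week 14 visit on Day 99 comes one day after it. The protocol schedule already implies this.

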**Table 3. Study Activities (Continued)**

- e. Physical examination performed at Screening, Week 12 and Week 56/Premature Discontinuation Visits are full physical examinations which must include an assessment of extra-intestinal manifestations (EIMs) and a count of the number of cutaneous fistulas. Physical examinations at all other visits are symptom based and must include a count of the number of cutaneous fistulas.
- f. Subjects with negative PPD test and/or QuantiFERON-TB Gold test within 90 days of Screening will not require a repeat skin test, if documentation is available. PPD skin test is to be read 48 to 72 hours after placement.
- g. Chest x-ray includes posterior-anterior (PA) **and** lateral views. Subjects with normal chest x-ray within 3 months of Screening would not require a repeat chest x-ray, if documentation is available.
- h. Subjects with normal ECG within 90 days of Screening would not require a repeat ECG, if documentation is available.
- i. Lab assessments will only need to be repeated at Baseline if the time between Screening and Baseline is greater than 14 days, or if the subject's health status has changed to warrant a repeat test.
- j. Dipstick urinalysis will be completed by the sites at all required visits. A microscopic analysis will be performed by the central laboratory, in the event the dipstick results show protein, ketones or blood greater than negative or glucose greater than normal. Further explanations of these tests are provided in the laboratory manual.
- k. Serum pregnancy test will be performed on all women of childbearing potential at Screening. Urine pregnancy test will be performed locally at Baseline Visit, and at the Week 12 and Week 56/PD for all women of child-bearing potential. The frequency can be increased up to every visit as per local regulations. If any urine pregnancy test is positive, a serum pregnancy test will be performed by the central laboratory.
- l. Subjects will be tested for the presence of the Hepatitis B Virus (HBV) at Screening. A positive result for the Hepatitis B surface antigen (HBs Ag) will be exclusionary. Please refer to hepatitis procedures for details on testing requirements. If required by country regulatory authorities to confirm eligibility, subjects will be tested for HIV and documented that the test has been performed. This testing is to be done at a local laboratory. A subject will not be eligible for study participation if test results indicate a positive HIV infection. AbbVie will not receive results from the testing and not be made aware of any positive result.
- m. Anti-dsDNA performed if ANA result is positive.
- n. If a sample cannot be obtained during the site visit, the site will give instructions and a stool sample supply kit (supplies will be provided at the time points indicated). The stool from which these samples are prepared should be scored using the Bristol stool chart by ePRO. All stool samples for metagenomic analysis should be collected before any bowel preparation for endoscopy is started and should be returned to the site within 3 days of collection.  
Note: The Screening stool sample may be taken anytime during the Screening period but should be collected prior to any bowel prep.
- o. Blood samples for the measurement of adalimumab and AAA concentrations will be collected prior to dosing. Testing of the adalimumab and AAA concentrations must not be performed locally. All pharmacokinetic results will remain blinded to the investigator, study site personnel and the subject throughout the study.

**Table 3. Study Activities (Continued)**

- p. Pharmacogenetic Marker and intestinal biopsy samples are optional. Separate consents must be signed prior to the sample draw. If the pharmacogenetic sample is not collected at Baseline, preferably it should be collected at the next study visit.
- q. Subject will begin corticosteroid taper at Week 4. If the Investigator feels that the steroid taper is not advisable for a particular subject at Week 4, the SDP should be consulted for evaluation and approval.
- r. Collection of SAEs begins the day the subject signs the informed consent.
- s. Administration of drug will be performed after all assessments and examinations scheduled for that day have been completed.
- t. Subjects will be contacted 70 days following study drug discontinuation for an assessment of any new or ongoing AEs, except those subjects that continue on adalimumab therapy after the end of study participation.
- u. The Screening results of the SFPS will serve as the Baseline value.
- v. Visits for dispensing new study drug in case of temperature excursion, loss or damage are not considered an Unscheduled Visit. In addition, visits to retest a lab will not be considered an Unscheduled Visit. Unscheduled Visits according to this table are for purposes when the subject is coming in for a visit for evaluation, assessment and potential dose escalation.

